We will enroll eligible, consenting pregnant women who are receiving sublingual BUP (subutex) in a supervised hospital or outpatient clinical setting because of their opiate addiction. Due to the possibility of limited subject availability at individual centers, recruitment can target subjects receiving pregnancy care at other institutions. Likewise, since buprenorphine is commonly not dispensed in a hospital setting, subjects may need to be recruited from clinics where buprenorphine is provided to pregnant women as part of a structured maintenance program. To facilitate enrollment, recruitment can target one or more specific aims as summarized below.

For Specific Aims 1 and 3:

We will recruit 40 eligible, consenting pregnant women to an 'extensive sampling' pharmacokinetic (PK) study in which they will be studied three times: once between 8 0/7-20 6/7, once between 21 0/7-35 6/7 and once at 4-6 weeks post-delivery. Studies done during pregnancy should be at least 12 weeks apart. We will also obtain patient demographics and medical history.

We will encourage subjects to complete as many PK studies as possible; however, subjects are only required to complete one PK study in order to participate in this portion of the study. Each study is 13 hours in length for BID dosing, 9 hours for TID dosing, 7 hours for QID dosing, and 6 hours for five times daily dosing.

Each PK study will be performed after the subject has been on a stable dose of BUP for a minimum of 7 days. Physiologic testing (pupillometry, galvanic skin response, and heart rate), COW and craving scores will be performed before the daily dose of BUP is taken.

Measurement Type	Dosing	Length of Study	No. of Measurements
Blood (BUP/metabolite)	BID	13 hrs	Baseline + 12 additional
Physiologic			Baseline + 9 additional
Blood (BUP/metabolite)	TID	9 hrs	Baseline + 12 additional
Physiologic			Baseline + 9 additional
Blood (BUP/metabolite)	QID	7 hrs	Baseline + 10 additional
Physiologic			Baseline + 7 additional
Blood (BUP/metabolite)	5 times/daily	6 hrs	Baseline + 10 additional
Physiologic			Baseline + 7 additional

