4. The relationship between maternal dose and concentration of buprenorphine and metabolites in umbilical cord, maternal and infant hair
5. The relationship between maternal plasma and breast milk concentrations of BUP and major metabolites
6. Cumulative amount of BUP and its metabolites excreted in breast milk.

c. Secondary Outcomes Neonatal:

Neonatal outcomes to be measured include the following:

1. Relationship between concentrations of BUP and its metabolites in maternal and umbilical cord plasma and maternal and newborn hair and maternal dose and parameters of neonatal withdrawal
2. Infant hospital days
3. Birthweight
4. Gestational age
5. Neonatal Complications including: Respiratory distress syndrome (RDS), stillbirth, neonatal death, intraventricular hemorrhage as determined by cranial ultrasound, bronchopulmonary dysplasia, necrotizing enterocolitis, early onset of neonatal sepsis, seizures, retinopathy of prematurity (ROP), and hyperbilirubinemia.

D.5.xiii. Statistical Considerations

Data Analysis Plan:

The primary outcomes will be the area under the plasma concentration x time curve (AUC) of BUP during early pregnancy compared to the AUC in late pregnancy. We will also compare the AUC of BUP and metabolites during early and late pregnancy and the post-partum period. Mixed-effect models, repeated measures ANOVA or paired t-testing, will be used to compare early to late-pregnancy and overall pregnancy values to the postpartum values. Secondary outcomes such as metabolite concentrations will be analyzed in the same fashion. Additional analysis will also include multiple regressions to evaluate the relationships between maternal and fetal plasma concentrations of BUP and its metabolites, placental p-glycoprotein, physiologic parameters and CYP3A4/5 expression. We will also use population pharmacokinetic analysis to evaluate the contribution of various covariates (i.e. maternal genotype, BMI, etc.) to the observed variability in the trough plasma concentrations of BUP.

Primary Hypothesis

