Based on data from our recently completed study, the dose-adjusted AUC was 2.34 ± 1.82 (ng/ml).hr in pregnant women at a mean gestational age of 34 weeks. In postpartum women, the dose adjusted AUC was nearly 100% higher at 4.0 ± 2.8 (ng/ml).hr. We anticipate that the AUC in the first half of pregnancy will be somewhere between values of non-pregnant women and those of pregnant women in the latter part of pregnancy. The sample size required to demonstrate a 50% difference between the dose adjusted AUC in the first half of pregnancy and the second half of pregnancy as well as a 50% difference between the dose adjusted AUC in the first half of pregnancy and the postpartum state is 37 ($\alpha = 0.05$, $\beta = 0.80$). We will recruit an additional 3 subjects to

account for dropouts or noncompliance. The secondary physiological outcomes will also be addressable with this sample size as the variance in pupil measurements is small (4.65 ± 0.4 mm at baseline and 2.64 ± 0.08 mm at 2 hours in the paper of Middleton et al¹³) and each patient will provide data from 2-3 PK studies. Thus there will be 120 studies that relate a physiologic variable to plasma buprenorphine. Specific Aim 5 which relates NAS to various parameters (maternal dose, maternal and cord plasma buprenorphine /metabolite concentrations etc.) can be addressed with the projected sample size as correlations between the dependent variable NAS and the numerous independent variables i.e. maternal dose, maternal concentration at delivery, maternal hair concentration, cord blood concentration, newborn hair concentration etc. can be performed with samples size of 15. We assume that 50 % of these infants will have some degree of NAS so the sample size of 40 should be sufficient. If the prevalence of NAS is lower, we can recruit additional subjects. Since the extensive PK studies will not be required to test this hypothesis, recruitment should be easier and can be done at secondary sites if needed.

Secondary Hypotheses

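### The named postpartum test uses an undefined and unsized overall-pregnancy value, while the sized early-pregnancy-versus-postpartum contrast is not named as a test

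*Combined protocol and SAP*

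**What the plan says.** **Sizing (D.5.xiii, Primary Hypothesis).** The required number is the one needed to "demonstrate a 50% difference between the dose adjusted AUC in the first half of pregnancy and the second half of pregnancy" and "as well as a 50% difference between the dose adjusted AUC in the first half of pregnancy and the postpartum state is 37". Three more women are added, giving 40.

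**Analysis (D.5.xiii, Data Analysis Plan).** Early versus late pregnancy AUC is the primary outcome. A second sentence adds a comparison across early pregnancy, late pregnancy and postpartum, without listing contrasts. A third offers mixed-effect models, repeated measures ANOVA or paired t-tests, which "will be used to compare early to late-pregnancy and overall pregnancy values to the postpartum values".

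**Paired test (D.5.xiii, Secondary Hypotheses).** Pregnant and postpartum non-compartmental parameters, AUC among them, are to be compared with a paired t-test, with a reference back to the earlier description.

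**Visits (D.1).** Three PK studies are planned and encouraged, but "subjects are only required to complete one PK study in order to participate in this portion of the study". D.4 and D.5.iii repeat this. Entry criterion 7 in D.4.i allows the single study to be in pregnancy or postpartum.

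**Primary question (D.2).** It asks whether exposure differs within pregnancy and between pregnancy and the postpartum state, so the postpartum comparison is part of the primary question.

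**The concern.** For the postpartum half of the primary question, the contrast that was sized and the contrast that is named as a test are different quantities. Overall pregnancy could mean the average of a woman's two pregnancy visits, whichever visit she has, or a model-based average. These agree only if early and late AUC are equal, and the Primary Hypothesis text expects early AUC to lie between the late-pregnancy and non-pregnant values.

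A paired t-test needs one pregnancy value per woman. Among women with a postpartum visit, some may bring only an early value, some only a late one and some both. No rule says what to do. Two analysts could follow the plan and report different pregnancy-to-postpartum changes from the same data, and the choice could be made after the data are seen.

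**Working it through.** **1. The plan's own figure.** Inputs from D.5.xiii, Primary Hypothesis: late pregnancy, "the dose-adjusted AUC was 2.34 ± 1.82 (ng/ml).hr in pregnant women at a mean gestational age of 34 weeks"; postpartum, "the dose adjusted AUC was nearly 100% higher at 4.0 ± 2.8 (ng/ml).hr"; alpha 0.05; the stated beta of 0.80, read as 80% power. Two-sided testing is assumed. Taking 50% of the late mean as the difference, 0.5 × 2.34 = 1.17, the two-sample normal formula gives

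n = 2 × (1.960 + 0.842)² × 1.82² / 1.17² = 37.98, so 38.

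This is one away from the stated 37; power at 37 is 0.79. The match is not unique. A paired t-test with a difference of 1.33 (4.0 − 4.0/1.5) and an SD of differences of 2.8 gives 37. So does a paired t-test with a difference of 1.17, SDs of 1.82 and 2.8, and an assumed within-woman correlation of 0.5. The protocol gives no formula, but none of these routes uses an overall-pregnancy value.

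**2. The early mean.** No early value exists; D.6 says none of the pilot women was studied in the first half of pregnancy. Three assumptions:

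- 2.67 = 4.0/1.5, if the sized 50% early-to-postpartum difference holds
- 3.17 = (2.34 + 4.0)/2, the midpoint
- 3.51 = 1.5 × 2.34, if the sized 50% early-to-late difference holds

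**3. Effect of the visit mix.** Let f be the average weight on early values among women who have a postpartum visit: the share with an early visit only, plus half the share with both. Half late-only and half both gives f = 0.25. Half early-only and half both gives f = 0.75.

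Pooled pregnancy mean = f × early + (1 − f) × 2.34. Gap = 4.0 − pooled mean. Ratio = 4.0 / pooled mean.

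| Early mean (assumed) | f | Pooled mean | Gap | Ratio |
|---|---|---|---|---|
| 2.67 | 0.25 | 2.42 | 1.58 | 1.65 |
| 2.67 | 0.50 | 2.51 | 1.50 | 1.60 |
| 2.67 | 0.75 | 2.59 | 1.41 | 1.55 |
| 3.17 | 0.25 | 2.55 | 1.45 | 1.57 |
| 3.17 | 0.50 | 2.76 | 1.25 | 1.45 |
| 3.17 | 0.75 | 2.96 | 1.04 | 1.35 |
| 3.51 | 0.25 | 2.63 | 1.37 | 1.52 |
| 3.51 | 0.50 | 2.93 | 1.08 | 1.37 |
| 3.51 | 0.75 | 3.22 | 0.78 | 1.24 |

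At the midpoint, the reported postpartum increase runs from 57% to 35% with no change in any woman's pharmacokinetics. If the early mean is close to the late one (2.67), the movement is small: 65% to 55%.

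**4. Power.** Paired t-test, 37 complete pairs, early mean 3.17, early SD assumed equal to 1.82, within-woman correlation assumed 0 to 0.7: power is 31% to 69% for early versus postpartum and 67% to 98% for the two-visit mean versus postpartum. Under these assumptions the pooled contrast is the easier one.

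**The case against.** - **Sizing and analysis are not disconnected.** A reader might infer that the study was sized for something it never tests. That is not so: early versus late is sized, named as a test and declared primary.
- **Early versus postpartum is not dropped.** The Data Analysis Plan promises a comparison across all three periods, and two of its listed methods could supply this contrast. This stands. The contrast is not excluded; it is just not named.
- **Single-visit women do not distort a paired test.** A woman with one visit has no pair and drops out. This also stands. The visit mix enters only through women who have a postpartum visit plus an early one, a late one or both.
- **Dependence on the mix is avoidable.** A mixed model with a fixed-weight contrast of period means has a fixed target. True, but the plan neither selects that model nor defines the contrast, and the later text points to a paired t-test.
- **The extremes overstate the size.** At the midpoint early mean, all-late and all-early pools give ratios of 1.71 and 1.26. A pool that extreme would leave the primary early-late comparison without data. Women are also encouraged to complete every study, and PK entry before 19 6/7 weeks falls inside the early window. The 25% to 75% range is the fairer one.
- **Other routes exist.** Gestational age is a covariate in the population PK model. That helps describe exposure across pregnancy, but it does not define the overall-pregnancy test.
- **The link to dosing is indirect.** Section A says postpartum dose reduction will be evaluated, but does not say that this pooled test will guide it. The case here rests on D.2 alone.

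**Conclusion.** The point holds in a limited form. For the postpartum part of the primary question, the plan names a test on a quantity that it neither defines nor sizes, and it does not name the postpartum contrast that it did size. If the paired test or a raw pool of observed values is used, the estimate depends on which pregnancy visits are available. The ratio is 1.57 to 1.35 at an early mean of 3.17 and 25% to 75% early weight, and about 1.65 to 1.24 over early means of 2.67 to 3.51.

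This rests on the pilot means, on assumed early means, and on an illustrative range for the visit mix. If early AUC lies between late and postpartum, as the protocol expects, postpartum remains higher in every case. The interpretation and size of the effect are at issue, not its direction.

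A reader might go on to infer that the pooled test is underpowered. The documents do not support that, and the calculation above points the other way under its assumptions. The change should be made because it fixes part of a primary comparison in advance at almost no cost.

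**What to change.** In D.5.xiii, in both the Data Analysis Plan and the Secondary Hypotheses text:

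1. Specify one mixed model for AUC with period (early, late, postpartum) as a fixed effect and a random subject effect, using all available PK visits. This replaces the open choice of three methods and the later paired t-test.
2. Name early-late and postpartum-early as the sized contrasts.
3. Name postpartum-late as supportive and label it as not sized.
4. Define any overall-pregnancy value as the equal-weight average of the two model-based period means, or report it as descriptive only.

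The cost is wording and minor analysis work, with no new visits or samples. The drawback is one additional unsized contrast, which the label makes plain. The model fixes the target of the comparison, but it still assumes that whether a visit is missed is unrelated to the unseen AUC, given the data observed. The plan should say so.

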For those women who are breast-feeding during the postpartum PK visit and wishing to participate in the breast feeding component, and if the CRC allows infants to come to the unit with their mothers, we will obtain breast milk at baseline prior to the morning BUP dose and approximately every 2-4 hours post dosing using an automated breast pump to empty the breasts. We will use at least 1 mL but not more than 5 ml of the milk for analysis of drug and metabolite concentrations and allow the mother to use the remaining milk for her infant. If these women participated in the post delivery ancillary study of breast milk, they can still participate in the postpartum PK breast milk study.

For those women consenting to the postpartum PK study, we will obtain infant blood by heel stick once prior to a feeding and again 1 hour after the feeding. Optimally this will be done during the feeding that is as close to the BUP dose as possible. In total, no baby will have more than 8 heel sticks, 6 while in the hospital or during a postpartum PRC visit as part of the postpartum ancillary study and 2 in the postpartum PK study. If the subject is not participating in the BUP PK study, the baby will have up to a maximum of 6 heel sticks (trough and peak levels on 3 occasions) as part of the postpartum ancillary study.

Upon completion of all biological fluids collection, the venous catheter will be removed and the subject will be discharged to home.

D.5.vii. Physiological Testing (Applicable to Subjects in the PK Study):

Pupillary diameter will be determined using a hand held pupillometer device (PLR-200™ Pupillometer- Neuroptics Irvine Cal.), galvanic skin response will be obtained using the Mind Ware Mobile Impedance Device, heart rate and blood pressure will be recorded by standard means. The Cravings and COW scores will be performed in conjunction with physiologic assessments at the following times:

Sample/Measurement Type	Dosing	Time Interval
physiologic	BID	Baseline and 30, 60, 90, 120, 240, 360, 480, 600, 720 minutes post dose
physiologic	TID	Baseline and 30, 60, 90, 120, 240, 300, 360, 420, 480 minutes post dose
physiologic	QID	Baseline and 30, 60, 90, 120, 240, 300, 360 minutes post dose
physiologic	5 times/day	Baseline and 30, 60, 90, 120, 180, 240, 300, minutes post dose

D.5.viii. Dietary Restrictions (Applicable to Subjects in the PK Study):

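### The plan relates plasma BUP to the physiologic markers by multiple regression with no term for woman or visit, and supports this with 120 studies that come from only 40 women

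*Combined protocol and SAP*

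**What the plan says.** The Data Analysis Plan in D.5.xiii names methods for two kinds of question.

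- For differences between periods: "Mixed-effect models, repeated measures ANOVA or paired t-testing, will be used to compare early to late-pregnancy and overall pregnancy values to the postpartum values". The next sentence extends this approach to secondary outcomes, with metabolite concentrations as the example.
- For relations between variables: "Additional analysis will also include multiple regressions to evaluate the relationships between maternal and fetal plasma concentrations of BUP and its metabolites". The list in that sentence continues with "placental p-glycoprotein, physiologic parameters and CYP3A4/5 expression". It states no unit of analysis, subject term or error structure.

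The relation of COW and craving scores, pupillometry, heart rate, blood pressure and GSR to plasma BUP and metabolites is the first secondary maternal outcome in D.5.xii(b), and it serves Aim 3.

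On size, D.1 says "We will recruit 40 eligible, consenting pregnant women" for the PK study. The Primary Hypothesis text in D.5.xiii says that "each patient will provide data from 2-3 PK studies" and concludes: "Thus there will be 120 studies that relate a physiologic variable to plasma buprenorphine". D.1 also says that "subjects are only required to complete one PK study in order to participate in this portion of the study".

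Within one visit, D.5.vii takes physiologic measurements repeatedly. For twice-daily dosing the schedule is "Baseline and 30, 60, 90, 120, 240, 360, 480, 600, 720 minutes post dose", which is 10 sets; TID also has 10, and QID and five-times-daily dosing have 8.

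**The concern.** The data for Aim 3 are repeated on two levels: visits within a woman, and time points within a visit. A woman's pupil size or skin response is likely to be partly her own stable trait. So is her BUP level, since each woman takes her own prescribed dose and Aim 2 presumes that lasting characteristics such as genotype drive exposure. A regression whose standard errors assume independent rows treats a second or third visit from the same woman as new evidence. Its confidence intervals are then too narrow, and a marker can look related to BUP because the same women recur in the data.

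Aim 3 looks for an objective measure to help gauge dosing, so an overconfident slope matters. The sample-size text points the same way: it counts studies and makes no allowance for correlation within a woman.

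**Working it through.** **1. The plan's figure.** 40 women × 3 visits = 120, so the stated count is reproduced, but only as a maximum.

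- Two to three studies each: 40 × 2 = 80 to 40 × 3 = 120.
- The 37 women in the sample-size calculation, before the 3 added for dropout: 37 × 2 = 74 to 37 × 3 = 111.
- One study each, the minimum in D.1: 40.

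**2. Effect of ignoring the woman.** Take *m* studies per woman, one value per study, no true relation, and within-woman intraclass correlations ICCx (BUP) and ICCy (marker). The variance of the slope is understated by the design effect

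DE = 1 + (m − 1) × ICCx × ICCy,

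and a nominal two-sided 5% test rejects with probability 2[1 − Φ(1.96/√DE)]. The documents give no ICC, so the values below are assumptions, set equal in both variables. The simulations used 40 women and 20,000 runs per row.

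| Studies per woman | ICC (both) | DE | Formula | Simulated |
|---|---|---|---|---|
| 3 | 0.3 | 1 + 2 × 0.09 = 1.18 | 7.1% | 7.0% |
| 3 | 0.5 | 1 + 2 × 0.25 = 1.50 | 11.0% | 10.6% |
| 3 | 0.7 | 1 + 2 × 0.49 = 1.98 | 16.4% | 16.4% |
| 2 | 0.3 | 1 + 0.09 = 1.09 | 6.1% | 5.7% |
| 2 | 0.5 | 1 + 0.25 = 1.25 | 8.0% | 7.6% |
| 2 | 0.7 | 1 + 0.49 = 1.49 | 10.8% | 11.1% |

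With m = 1, or with either ICC at zero, DE = 1 and the rate stays at 5%. With three studies and both ICCs equal to 1, DE = 3 and the ceiling is 25.8%.

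**3. What 120 studies are worth for a slope.** 120/DE gives 120/1.18 = 102, 120/1.50 = 80 and 120/1.98 = 61 at ICC 0.3, 0.5 and 0.7.

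**4. If time points were pooled as well.** The maximum is 40 × 3 × 10 = 1,200 rows, or 30 per woman. With equal correlation among all of a woman's rows, DE = 1 + 29 × 0.09 = 3.61 at ICC 0.3 and 1 + 29 × 0.25 = 8.25 at ICC 0.5. The formula gives 30% and 50%; simulation (2,000 runs) gives 29% and 50%.

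**5. Does a woman term cure it?** For 40 women × 3 studies, a random intercept for woman gave 5.0% at ICC 0.5 and 6.3% at ICC 0.8 (600 runs each). A within-woman (fixed-effect) model stayed at about 5% throughout. Cluster-robust standard errors gave 5.6% to 6.7%.

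**The case against.** The strongest reply is that the plan never says the rows are independent.

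- **The method is open.** The regression sentence gives no unit of analysis. It also covers cord-blood and placental quantities, which exist once per woman, so a model containing them would have one row per woman. This stands: ordinary regression on 120 rows is an inference from silence.
- **The plan may already bring in mixed models.** Secondary outcomes are to be analysed like the primary one, and the physiology–concentration relation is a secondary outcome. This is weaker. The methods carried over are assigned to period comparisons. A paired test of early against late pregnancy does not relate pupil size to concentration, and the next method sentence puts physiologic parameters under multiple regression.
- **The 120 is not the formal sample size.** The text first calls the physiologic outcomes addressable with the 40 women and cites the small variance of pupil measurements; the study count follows. This stands in part. The count is still offered as support, as a maximum and without qualification.
- **Aim 3 is exploratory.** It evaluates potential endpoints, D.3 warns that numbers may be too small for some questions, and alpha 0.05 appears only for the AUC sample size. This stands, and it limits the stakes. Intervals that are too narrow mislead even without a formal test.

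A reader might go further and infer that Aim 3 will declare a marker far more often than 5% when none exists. The documents do not support that. At one value per study it needs high correlations in both variables. The 29–50% rates need pooling of time points, which no section specifies.

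A reader might also infer that at least one false marker is likely among the six measures. Treated as independent, six markers give 1 − 0.95^6 = 26% with correct tests, and 1 − 0.93^6 = 35%, 1 − 0.89^6 = 50% and 1 − 0.84^6 = 65% at the three ICCs. The first 26% is multiplicity, which a random effect does not remove. The plan also states no rule for selecting a marker.

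**Conclusion.** The point holds as a gap in specification that has a known consequence. For the physiology–concentration relation the plan names only multiple regression, says nothing about repeated visits or time points, and cites 120 studies where the design guarantees between 40 and 120 from 40 women. If the repeats are treated as independent, the false-positive rate per marker at a nominal 5% is about 7% to 16% with three studies per woman and about 6% to 11% with two, over assumed ICCs of 0.3 to 0.7 in both variables. There is no inflation if either variable is uncorrelated within woman or if each woman gives one study.

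These figures assume equal correlation among a woman's studies and no time course shared across women. A shared post-dose or period trend could add spurious association that a random intercept alone would not remove. The calculation also supplies the 5% test, since the documents set none for Aim 3.

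**What to change.** In the Data Analysis Plan of D.5.xiii, replace multiple regression for the physiologic, COW and craving measures with a linear mixed model of each measure on plasma BUP and metabolites. Include a random effect for woman and, when within-visit time points are used, for visit within woman. State which unit, study or time point, each analysis uses. Multiple regression can remain for quantities measured once per woman.

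In the Primary Hypothesis text of D.5.xiii, replace the 120 studies with 40 women who each contribute one to three repeated studies (at most 120 in all), and do not present 120 as independent units.

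The cost is wording only. Mixed-effect models are already named for the period comparisons, and no new data or visits are needed. The downside is that the stated information for the physiologic outcomes becomes less favourable. The nested form was simulated only 150 times (2% rejection), too few to show that it is well calibrated, so a larger simulation before it is adopted would be sensible.

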We have developed a HPLC-MS-MS assay for BUP and metabolites with a lower limit of quantitation of the assay for BUP (BUP), of 0.05 ng/ml, while that for nor-BUP is 0.5 ng/ml. We have performed an intensive PK study on 12 subjects. The dose-adjusted AUC in the third trimester of pregnancy (2.4 ng/ml).hr was lower than in the postpartum period (4.0 ng/ml).hr while clearance is higher in pregnancy (589 L/hr) than in the postpartum period (288 L/hr). There was a large variation (cv = 50%) in both AUC and clearance values. None of the subjects in this cohort was studied in the first half of pregnancy.

D.7. Potential Problems, Alternative Strategies, Benchmarks

Recruitment is a potential problem in any clinical trial and if other sites in the OPPTB do not have access to patients on BUP in their own institutions they may have difficulty recruiting subjects. These patients have difficulty with compliance to drug treatment regimens so dropout may be higher than in most clinical trials. Postpartum studies are difficult because of childcare issues and this may hamper recruitment. These challenges can be overcome by identifying physicians and clinics that write prescriptions for BUP and care for such patients. The childcare issue can be addressed by financial incentives or by allowing the mother to bring her baby to the CRC during study days.

D.8. Feasibility

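### Postpartum AUC is 71% above the late-pregnancy value, not nearly 100%, and the two 50% differences behind n = 37 cannot both hold on the plan's own AUC means

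*Combined protocol and SAP*

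**What the plan says.** Section D.5.xiii (Statistical Considerations), under Primary Hypothesis, takes its inputs from a recently completed study. Dose-adjusted AUC was 2.34 ± 1.82 in women at a mean of 34 weeks, and then: "In postpartum women, the dose adjusted AUC was nearly 100% higher at 4.0 ± 2.8 (ng/ml).hr". No early-pregnancy value is given, but a range is: "We anticipate that the AUC in the first half of pregnancy will be somewhere between values of non-pregnant women" and those of women late in pregnancy. The sample size is meant to show a 50% difference between the first and second halves of pregnancy, "as well as a 50% difference between the dose adjusted AUC in the first half of pregnancy and the postpartum state is 37", with α = 0.05 and a figure of 0.80 labelled β. Three women are added, giving 40.

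Under Data Analysis Plan, the same section makes the primary outcome the AUC "of BUP during early pregnancy compared to the AUC in late pregnancy". It adds a comparison of AUC across early pregnancy, late pregnancy and postpartum, and says that mixed models, repeated-measures ANOVA or paired t-tests "will be used to compare early to late-pregnancy and overall pregnancy values to the postpartum values".

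Section D.6 reports a 12-subject intensive study with AUC of 2.4 in the third trimester and 4.0 postpartum. It adds "There was a large variation (cv = 50%) in both AUC and clearance values" and "None of the subjects in this cohort was studied in the first half of pregnancy". Sections D.1, D.4, D.4.i, D.5.iii and D.5.iv require each woman to complete only one PK study.

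**The concern.** The paragraph that justifies the sample size for the primary outcome contains a percentage that its own means do not give. It then asks for two differences that would fit only if postpartum AUC were at least twice the late-pregnancy value. With early pregnancy placed between the other two periods, the early-late and early-postpartum differences have to share one gap, so enlarging one shrinks the other. If that gap is too small for both, a reader cannot tell which contrast, if either, has the 80% power claimed for 37 women. Early versus late is the primary contrast, and early pregnancy is the period with no pilot data.

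**Working it through.** **Inputs.** Late pregnancy 2.34, SD 1.82; postpartum 4.0, SD 2.8; two 50% differences; n = 37; α = 0.05 (taken as two-sided); power 0.80 (D.5.xiii). Late pregnancy 2.4; CV 50% (D.6).

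**The plan's 37.** For two independent groups, n per group = 2 × (1.96 + 0.8416)² × (SD/d)².
- d = 0.5 × 2.34 = 1.17, SD 1.82: 15.70 × 2.420 = 37.98, so 38.
- d = 0.5 × 2.4 = 1.20, SD 1.82: 36.11, so 37.

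The plan's number is therefore approximately what an unpaired formula gives for one difference of half the late-pregnancy value. The documents do not say that this formula was used.

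**The percentage.** 4.0/2.34 = 1.709, so 71% higher. With 2.4, 4.0/2.4 = 1.667, so 67% higher.

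**Can both 50% differences hold?** The total gap is 4.0 − 2.34 = 1.66.
- Early 50% above late: 2.34 × 1.5 = 3.51. Then 4.0/3.51 = 1.14, so postpartum is 14% (0.49) above early.
- Postpartum 50% above early: 4.0/1.5 = 2.67. Then 2.67/2.34 = 1.14, so early is 14% (0.33) above late.
- Two steps of half the late value: 1.17 + 1.17 = 2.34, against a gap of 1.66. This needs a postpartum/late ratio of 2.0.
- Two successive 50% rises: 1.5 × 1.5 = 2.25. The ratio is 1.71.
- 50% measured down from the higher value: early would be 2.0 (half of 4.0), below the expected range, or 4.68 (twice 2.34), above it.

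No base for the percentage makes both fit. The largest difference that both contrasts can share is 35.5% of the late value (0.83/2.34), at the midpoint 3.17.

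**Consequence for power.** The two differences sum to 1.66, so the smaller is at most 0.83. The early-late difference reaches 1.17 only if early lies at least 1.17/1.66 = 70% of the way from late to postpartum, and early-postpartum is then at most 0.49. Power by t-test:
- Unpaired, 37 per group, SD 1.82: 78% at 1.17, 49% at 0.83.
- Paired, 37 pairs, with the SD of differences (2.47) that gives 80% at 1.17: 51% at 0.83.

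**Illustration only: paired power.** Assumptions not in the documents: early AUC at the midpoint 3.17, early SD interpolated between the other two, one common within-woman correlation from 0 to 0.7, raw-scale normality (rough at these CVs), complete sets only. At the midpoint, overall pregnancy versus postpartum differs by 4.0 − (2.34 + 3.17)/2 = 1.245.

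| Contrast | Spread used | 37 women | 30 women | 20 women |
|---|---|---|---|---|
| Early vs late, 0.83 | SDs in D.5.xiii | 39–84% | 32–75% | 22–56% |
| Early vs late, 0.83 | CV 50% (D.6) | 70–99% | 61–97% | 43–87% |
| Overall pregnancy vs postpartum, 1.245 | SDs in D.5.xiii | 64–98% | 55–95% | 39–82% |
| Overall pregnancy vs postpartum, 1.245 | CV 50% (D.6) | 91% or more | 84% or more | 66–98% |

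The choice of spread matters. The SDs in D.5.xiii imply CVs of 1.82/2.34 = 78% and 2.8/4.0 = 70%, against 50% in D.6.

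**The case against.** The strongest reply is that the two 50% figures are separate detectable differences, not effects expected together. Early-late at 1.17 is coherent taken alone: 3.51 lies inside the expected range and 37 is approximately right for it. Half of the postpartum value, 2.0 with SD 2.8, would need only 31 per group. The first part stands. The second does not help, because a difference of 2.0 exceeds the whole gap of 1.66. The paragraph also derives its expectation for early pregnancy from these same means, so a reader will take the effects to come from them.

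A second reply is that the pilot is imprecise. This stands too. If each mean rests on the 12 subjects of D.6, the standard error of the gap, treated as unpaired, is √((1.82² + 2.8²)/12) = 0.96, and the 95% interval is −0.34 to 3.66. A gap of 2.34 lies inside it. The stated effects conflict with the plan's point estimates; the data do not rule them out.

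A third concerns pairing and follow-up. Women serve as their own controls, D.1 encourages as many PK studies as possible, dismissed women are replaced (D.5.iii), and a mixed model can use incomplete women. Power could therefore exceed the unpaired figures.

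Three stronger readings are tempting and not supported:
- That the AUC and clearance figures contradict each other. Clearance does roughly double in D.6 (589/288 = 2.05), which may explain the wording, but a ratio of mean clearances need not equal a ratio of mean AUCs. Even 2.05 is below the 2.25 that two successive 50% rises need.
- That the plan sizes one postpartum contrast and tests only another. The Data Analysis Plan also compares all three periods, so the mismatch is partial: overall pregnancy versus postpartum simply has no stated power.
- That the CVs are a proven contradiction. The documents do not say that the study in D.5.xiii is the one in D.6.

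**Conclusion.** The point holds, as a fault in the stated assumptions. The increase is 71%, and on the plan's AUC means the two 50% differences cannot both occur with early pregnancy in between. On the unpaired basis that reproduces 37, at most one of the two contrasts has the stated 80% power. The smaller difference is at most 0.83, where a design with 80% power at 1.17 has about 50%.

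A reader might infer that 37 is a miscalculation or that the trial is underpowered. Neither follows. The number is approximately recoverable for one difference of 1.17 to 1.20. True power depends on a within-woman SD and on the count of women with both visits, which the documents do not give. So 37 may be enough, but the plan does not show it. The conclusion rests on the pilot point estimates, the plan's own placement of early pregnancy between the other periods, and a two-sided test. It should be fixed, because it is the sample-size basis for the primary outcome.

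**What to change.** In D.5.xiii, under Primary Hypothesis:

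1. Replace the description of postpartum AUC as almost double with 71% higher.
2. State the base of the 50%.
3. Either name early versus late as the one contrast sized at 50% of the late value (1.17), or replace the two 50% differences with ones that fit between 2.34 and 4.0. A split of 0.83 each is only an example; no early-pregnancy data support the midpoint.
4. Restate power for early versus late and for the postpartum comparison by a paired calculation. Give it as a range over an assumed within-woman correlation and over the number of women expected to have both visits, since only one PK study is required. Say which SD or CV is used, and why D.5.xiii and D.6 differ.
5. Write power = 0.80 in place of β = 0.80.

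The cost is one paragraph, one recalculation, and possibly a less favourable stated power. The restatement itself needs no extra patients.
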